The primary substance abuse outcomes (self-reported abstinence) will be assessed throughout the study and through a six month follow-up. Additional outcomes will include use of other services (medical, legal), patient and provider satisfaction, as well as the costs of implementing the program. Each week, the counsellors will deliver a questionnaire (provided by the CHCR) which covers this range of topics to their patient participating in the trial. The data will be analyzed with a focus on feasibility (retention in both conditions, levels of substance abuse, health problems, and cost by condition).

4. SUBJECT SELECTION:

Participants will be recruited from Prince Edward Island; Lennox Island Health Centre and Abegweit Health Centre, Mount Herbert Provincial Addictions Treatment Facility Transition Unit and Methadone clinic, Holland College Student Services, University of Prince Edward Island Student Services, Charlottetown Methadone Clinic and Prince County Hospital. At RECAP in New Brunswick and Ontario Shores Mental Health Centre in Ontario.

A total of 240 Participants will be recruited during years 1-2 and an additional 440 participants will be recruited during years 3-4 ending in April 2019.

Counsellors already employed by the Centres will recruit participants who are willing to consent to a randomized trial of CBT4CBT. In order to create as representative a sample as possible, the inclusion criteria will be fairly broad, including any consenting individual who reports substance abuse in the past thirty days. Individuals who are currently suicidal, homicidal, or require immediate hospitalization will be excluded.

The participants will be patients who have reported substance abuse in the past thirty days. For the initial trial, all participating individuals will be over eighteen years of age and be approved to participate by their addictions counsellors.

Counsellors will ask individuals seeking treatment for substance abuse if they would be interested in learning about and participating in a substance abuse treatment project. If yes, participants will be introduced to the study Research Assistant who will go through the consent form(attached) with them. The Research Assistant will orally read the forms if necessary and individuals will be informed of their right to withdraw from the program should the need arise.

5. RESEARCH PLAN:

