The individuals recruited for this study will each fall into one or more subgroup of the trial (transitioning patients [inpatient to outpatient], youth [18-24 years], maintained on methadone, and indigenous individuals) and will be analyzed individually as well as collectively by compiling results from all sites. A subgroup analysis based on gender is also planned to investigate any differences in outcomes between male and female participants, these two groups, historically, can show significant differences in response to mental health and addictions treatment.

Participants will be randomized to either test or control groups. Participants in the control group will receive treatment as usual (the conventional treatment offered at that site) and will also meet with the Research Assistant during week 4 and week 8 to complete questionnaires (attached) either in hard copy or online on a tablet provided. These participants will also be contacted six months after their eight-week participation in the trial ended to complete a follow-up questionnaire.

Participants randomized to the test group will receive treatment as usual but will also be asked to spend at least thirty minutes per week using the program. CBT4CBT use by each participant will be monitored throughout the trial to ensure that this requirement is being met. They may choose to do this on location at the site or from their personal computer/tablet. The individuals in this arm of the trial will also meet with a Research Assistant once a week for eight weeks to complete questionnaires and will be contacted six months after their eight-week participation in the trial ended to complete a follow-up questionnaire. These questionnaires can be completed online. Each participant will be asked to participate in the eight-week long treatment period regardless of group (test or control). In addition to participants' treatment as usual, this will involve a

commitment of approximately 10 minutes as a weekly average from participants in the control group, and approximately 45 minutes as a weekly average from participants in the test group. Please see the consent form table outlining the time commitments in more detail.

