This trial design will mirror the designs in the trials already successfully conducted in the United States. Once an individual consents to participate, the counsellor will contact the Research Assistant who will meet with the individual and assign them a participant number generated using Randomizer.org (Geoffrey C. Urbaniak, 2015). This number will have been previously assigned to either test or control. The participant will be notified about the trial arm that they are placed into so that their participation may commence.

A Research Assistant will deliver the questionnaires to the trial participants. Questionnaires may be answered in hard copy or online in private. This removes the pressure from the participants to 'improve' in the eyes of their counsellor. Other than the addition of sections specifically relating to the CBT4CBT program, the questionnaires between groups will be identical.

As mentioned above, three previous/pilot studies in urban areas of the U.S. have been performed ([name] et al., 2008, 2009, 2014). The trial described herein will follow a very similar design.

Questionnaires, data analysis and protocols are based on those previously used by our collaborator in the US and have all been tailored to better suit Canadian populations. Based on the significant success that [name] had using these outcomes, tools and protocols we are confident in their reliability and validity.

Individuals who consent to this trial will be notified at the beginning of the trial that they have the right to remove themselves from the trial at any time. They also have the right to contact their counsellor or either co-investigator (phone numbers and emails provided on the consent form) at any time should they have questions or concerns. The counsellors also hold the ability to remove any of their patients from the trial at any time if they see fit.

6. ANALYSIS OF DATA:

Statistical analysis techniques previously used by the Co-Investigator [name] and her team will be performed on the generated data from this trial ([name] et al., 2008, 2009, 2014). These include one and two-way analysis of variance (ANOVA's) where appropriate. This will ensure a relevant analysis approach is used for the field of addictions treatment research as well as ensuring that the generated results may be compared with those previously established at other sites.

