The power calculations performed to calculate the sample size are based on three similar published trials of CBT4CBT in urban populations in the US. Primary outcome measurements of this trial will be a subset of measurements collected in these previous trials. We believe retention and follow up rates will be similar if not higher than the previous trials as PEI has a less transient community than most urban centers like Connecticut. Based on the three previous trials ([name] et al., 2008, 2009, 2014), the average drug use measurement (measured by the percent days abstinence from all drugs) in the test groups was 75% and control group 66% with a common standard deviation of 24% at the end of the eight week trial. Retention during the eight week trial was on average 77% and follow-up success was approximately 87% six months post trial. These values were used to calculate the sample size of 30 (for each group) to achieve statistical significance with an alpha of 0.5 and a power of 0.8 for subgroup analysis of the initial trials on PEI, and an alpha 0.05 and a power of 0.8 for combined analysis (i.e. combining results from

all 240 participants across the four trial settings). Power calculations to achieve statistical significance with an alpha of 0.05 and a power of 0.9 were calculated for the large-scale effectiveness trials and a sample size of 110 was found.

Primary outcomes measured include retention, changes in drug use, changes in health (e.g. medical visits, family and social satisfaction, etc.) and program implementation costs. The outcomes to be determined are identical in the four parallel trials to foster comparability across populations.

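### The stated 90% power with a sample size of 110 does not follow from the plan's inputs: power in a single large-scale trial is about 0.79 if 110 is per group and 0.50 if it is the total

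*Combined protocol and SAP*

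**What the plan says.** Section 6 (Analysis of Data) introduces its sample-size paragraph with a general statement of source: "The power calculations performed to calculate the sample size are based on three similar published trials of CBT4CBT". It then gives one set of planning values, for the share of days without drug use: "in the test groups was 75% and control group 66% with a common standard deviation of 24% at the end of the eight week trial". It adds: "Retention during the eight week trial was on average 77% and follow-up success was approximately 87% six months post trial".

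Three calculations follow.

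- Subgroup analysis in the initial trials: 30 per group, printed alpha 0.5, power 0.8.
- Combined analysis of the initial trials: 240 participants, alpha 0.05, power 0.8.
- Large-scale effectiveness trials, alpha 0.05: "a power of 0.9 were calculated for the large-scale effectiveness trials and a sample size of 110 was found".

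No second set of means, standard deviation or adjustment is given for the third calculation. The figure of 30 has a unit ("These values were used to calculate the sample size of 30 (for each group"), but 110 has none. Section 4 (Subject Selection) says that "an additional 440 participants will be recruited during years 3-4". For the analysis, section 6 says of the planned techniques: "These include one and two-way analysis of variance". Section 5 (Research Plan) says that the subgroups "will be analyzed individually as well as collectively by compiling results from all sites".

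**The concern.** A 9-point difference with a standard deviation of 24 points is a standardized effect of 0.375. At two-sided alpha 0.05, an effect of that size needs about 113 per group for 80% power and considerably more for 90%. So 110 looks like an 80% design labelled as 90% if it is per group, and much weaker than that if it is the total.

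The missing unit matters in itself, because the two readings differ in power by about 0.30 and the reader cannot choose between them. The 440 in section 4 equals 2 trials x 2 groups x 110, but also 4 trials x 110.

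What is at stake is how a single trial is read. The plan intends individual as well as collective analyses, and section 6 aims to refine the program for each population. If one large-scale trial shows no significant difference, a reader who trusts the 0.9 would take that as stronger evidence of no benefit than it is.

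**Working it through.** **Inputs from section 6.** Means 75% and 66%, so a difference of 9 points; standard deviation 24 points; alpha 0.05; stated power 0.9; stated sample size 110.

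**Assumptions, not stated in the plan.** Equal allocation. Two-sided test; the ANOVA named in section 6 is, for two groups, equivalent to a two-sided t-test. One-sided results are shown as well. Complete data unless noted.

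**Standardized effect.** d = 9/24 = 0.375.

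**1. Can 110 be reproduced at alpha 0.05 and power 0.9?** By the normal approximation, n per group = 2(z₁₋α/₂ + z_power)²/d².

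- Two-sided, 90%: 2 x (1.960 + 1.282)²/0.375² = 149.4, so 150 (exact t-test 150.4, so 151).
- One-sided, 90%: 2 x (1.645 + 1.282)²/0.375² = 121.8, so 122 (exact 122.5, so 123).
- Two-sided, 80%: 2 x (1.960 + 0.842)²/0.375² = 111.6, so 112 (exact 112.6, so 113).

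The stated 110 does not reproduce at 90%, either as a per-group figure or as a total. It is close to the 80% requirement per group.

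**2. Power delivered.** Power ≈ Φ(d√(n/2) − 1.960). For n = 110 per group: 0.375 x √55 = 2.781, and Φ(0.821) = 0.794. For n = 55: 0.375 x √27.5 = 1.967, and Φ(0.007) = 0.503. The exact noncentral-t values are:

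| Reading | Two-sided | One-sided | Two-sided, 87% observed | Two-sided, 77% observed |
|---|---|---|---|---|
| 110 per group | 0.791 | 0.870 | 0.733 | 0.680 |
| 110 in total (55 per group) | 0.496 | 0.621 | 0.443 | 0.400 |
| All 440 pooled (220 per group) | 0.975 | 0.989 | 0.955 | 0.931 |

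Simulation gave 0.794, 0.500 and 0.976 for the two-sided column. The last two columns assume that outcomes are missing at the rates quoted in section 6; retention there may mean staying in treatment rather than providing data.

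**3. Do the plan's other figures reproduce by the same method?** Yes, with complete data: 30 per group at the printed alpha of 0.5 gives 0.798, and 240 in total (120 per group) at alpha 0.05 gives 0.825. Both match the stated 0.8. The 110 is the figure that does not fit.

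**4. What would give 0.9?** At 110 per group, two-sided, d must be 0.439. That means one of:

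- a difference of 0.439 x 24 = 10.5 points;
- a standard deviation of 9/0.439 = 20.5;
- baseline adjustment with a correlation of √(1 − (0.375/0.439)²) = 0.52.

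At 55 per group the difference must be 15.0 points. Separately, at alpha 0.5 the stated inputs with 55 per group (110 in total) give power of 0.906. None of these settings is stated for the large-scale trials.

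**The case against.** - **The inputs are not tied to 110 explicitly.** The sentence on 110 names no inputs; the explicit statement that the listed values were used belongs to the earlier calculations. Change in drug use is also listed as an outcome, and a baseline-adjusted calculation could give 110 per group. This stands as a limit: the firm conclusion is that 0.9 does not follow from what is stated, not that the true power is known to be 0.79 or 0.50. But the paragraph's opening sentence attributes the power calculations generally to the three earlier trials, and no other values are given.
- **The alpha may be the source.** At alpha 0.5, which the section prints for the subgroup calculation, 110 in total gives 0.9 almost exactly, and four trials of 110 make 440. This is unproven. If true, the printed alpha of 0.05 would be wrong instead, so the sponsor should be asked which alpha was used.
- **The cross-check ignores loss.** The other figures reproduce only with complete data; at 77% observed the pooled 240 gives 0.72. The 0.798 at 30 per group also counts rejections in the wrong direction; without them it is 0.782. Both points are correct, but loss only lowers the power at 110.
- **The pooled analysis is adequate.** It is, under complete data or either single rate. With both rates multiplied (0.77 x 0.87 = 0.67) it is 0.894, just under 0.9. But the text attaches 0.9 to 110, not to 440, and it says so explicitly when it means a combined analysis of the initial trials.
- **The consequence is partly inferred.** The individual analyses in section 5 are by subgroup, participants may belong to more than one, and no passage says how a null single trial would be read. That is fair, but it does not make the stated power correct.

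**Conclusion.** The concern holds. On the plan's only stated inputs, a large-scale trial with 110 per group has power of 0.79, and one with 110 in total has 0.50, against the stated 0.9. The corresponding chance of missing the 9-point effect is about 21% or 50%, not 10%. This rests on equal allocation, a two-sided test and complete data. A one-sided test (0.87 or 0.62) does not rescue the figure, and missing outcomes make it worse. The shortfall concerns single trials. The collective analysis of all 440 exceeds 0.9 with complete data or with either of the quoted retention rates applied alone. The missing unit for 110 is a second defect, and the documents do not resolve it. A stated power that fails on its own inputs should be corrected before any single-trial result is interpreted.

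**What to change.** In section 6, state whether 110 is per group or per trial, whether the test is one- or two-sided, and which alpha was actually used. Then do one of the following.

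1. Document the inputs that produced 110: difference, standard deviation and any baseline adjustment.
2. Replace 0.9 with the power delivered, for example:

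> With 110 [per group / in total] per large-scale trial, a 9-point difference, a standard deviation of 24, two-sided alpha 0.05 and complete data, power is about [0.79 / 0.50]. The collective analysis of all 440 participants (220 per group) has power of about 0.975, or about 0.93 if 23% of outcomes are missing.

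If 0.9 was meant for the collective analysis, say so. Add that a null result from a single trial will not be interpreted as if that trial had 90% power.

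The cost is wording in one section; recruitment does not change. The drawback is that, unless different inputs are documented, the stated power for individual large-scale trials becomes less favourable. If the sponsor does intend 90% per trial on the stated inputs, 110 is not enough (151 evaluable per group would be needed), but correcting the text does not require that choice.

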A collaboration has now been formed between [name] and Drs [name] and [name] of the UPEI Centre for Health and Community Research (CHCR) that will bring CBT4CBT to Canada. While CBT4CBT has previously been tested in urban areas, there are many advantages to offering computer-based training to more rural populations (such as PEI). These more remote areas frequently suffer from a lack of services, as well as a lack of continuity with the services currently offered. CBT4CBT may very well provide that needed continuity to Addictions treatment and has also been shown to improve retention.

3. BACKGROUND, RATIONALE AND STATEMENT OF RESEARCH QUESTION(S):

CBT4CBT will be the first computer-based, cognitive behavioural therapy program for Addictions treatment to be offered in Canada. CBT4CBT has been rigorously tested in urban populations in the United States but this collaboration will be the first pilot trial in First Nation and other rural communities in Canada. Prince Edward Island has a self-proclaimed need for innovative new substance abuse treatments and CBT4CBT may provide the continuity and retention to traditional therapy programs that current available treatment options often lack. This study will allow CBT4CBT to be tested in several Prince Edward Island communities to gage its efficacy and effectiveness. The results and feedback received from the pilot study will allow the program to be adapted for Canadian populations in order to optimize its positive outcomes within Canada.

CBT4CBT has been tested in urban populations in the United States in three rigorous randomized clinical trials with great success. The nature of CBT4CBT suggests it would also be beneficial in rural and remote populations which are common across Canada. Computer based treatments are cost-effective and although their nature necessitates human participants they have minimal risk associated with them. As the first computer based training for Addictions in Canada this research project could have broad implications for treatment in Addictions across our country.

Analysis techniques will be based on those used in previous CBT4CBT trials conducted by our collaborator, [name].

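### Sections 3 and 6 rank the same outcomes differently, and the plan implies but never declares the single outcome, time point and error rule behind the 0.05 combined analysis

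*Combined protocol and SAP*

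**What the plan says.** Section 3 (Background, Rationale and Statement of Research Question(s)) states: "The primary substance abuse outcomes (self-reported abstinence) will be assessed throughout the study and through a six month follow-up". It continues: "Additional outcomes will include use of other services (medical, legal), patient and provider satisfaction, as well as the costs of implementing the program". It then describes the analysis this way: "The data will be analyzed with a focus on feasibility (retention in both conditions, levels of substance abuse, health problems, and cost by condition". Retention appears only in that last sentence and is given no rank. Section 3 also calls the study the "first pilot trial in First Nation and other rural communities in Canada".

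Section 6 (Analysis of Data) states: "Primary outcomes measured include retention, changes in drug use, changes in health". Medical visits and family and social satisfaction are given as examples of health, and the sentence ends with implementation costs. The only outcome that Section 6 calls secondary is feedback from patients and counsellors, analysed qualitatively.

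The sizing paragraph of Section 6 uses percent days abstinent from all drugs: 75% in the test groups, 66% in the control groups, common SD 24%, at the end of the eight-week trial. It also cites 77% retention and about 87% follow-up at six months. It gives alpha 0.05 and power 0.8 for the combined analysis of 240 participants, without naming an outcome in that clause. One-way and two-way ANOVA are to be used where appropriate and are not assigned to outcomes.

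On assessments, Section 3 has counsellors delivering a questionnaire each week, with no distinction by arm. Section 5 (Research Plan) gives the task to a Research Assistant. Control participants "meet with the Research Assistant during week 4 and week 8 to complete questionnaires", while test participants "meet with a Research Assistant once a week for eight weeks to complete questionnaires".

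**The concern.** Implementation cost cannot be both an additional outcome and a primary one. The conflict over service use is close but not exact, because Section 3 speaks of use of medical services and Section 6 gives medical visits as an example of health. Nothing else in the plan settles the ranking.

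Section 6 therefore puts at least four outcomes on an equal footing beside a 0.05 analysis that was sized for one of them. The abstinence outcome itself is also not pinned down. Section 6 sizes a level at eight weeks but lists change in drug use, and Section 3 follows abstinence through six months. No testing order, adjustment or definition of success is given. Once data are seen, a favourable result on any listed primary, or on abstinence at either time, could be presented as the planned 0.05 finding. The stated error rate would then not describe the claim.

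**Working it through.** **1. The rankings side by side**

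| Outcome | Section 3 | Section 6 |
|---|---|---|
| Abstinence / drug use | primary | primary |
| Retention | unranked, within the feasibility focus | primary |
| Health / medical use | service use additional; health problems within the feasibility focus | primary, with medical visits as an example |
| Implementation cost | additional; also within the feasibility focus | primary |

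The cost row is a direct contradiction. Section 6 names four primaries, and because its list is open, four is a minimum.

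**2. Which outcome was sized?**

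Inputs from Section 6: difference 75 − 66 = 9 points, SD 24, so d = 9/24 = 0.375. Assumed: equal allocation (240/2 = 120 per arm, which fits 30 per group in each of four settings) and two-sided tests. Power is from the noncentral t, which for two arms equals one-way ANOVA.

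- The plan's subgroup figure: 30 per arm at the printed alpha of 0.5 gives power 0.798, matching the stated 0.8.
- The combined analysis: 120 per arm at 0.05 gives power 0.825, which meets the stated 0.8.
- Number needed for 80% at 0.05, normal approximation: 2 × (1.960 + 0.842)² / 0.375² = 111.6, so 112 per arm. With the t distribution it is 113 per arm (power 0.801).

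The figures fit abstinence alone with no allowance for dropout. Dividing by 77% retention would give 30/0.77 = 39 and 112/0.77 = 145.5, so 146 per arm, against the 30 and 120 planned. If only 77% were analysed (120 × 0.77 ≈ 92 per arm), power would be 0.716.

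Percent days abstinent is the only outcome with a between-arm difference, and the plan's numbers reproduce from it. The inference that it carries the 0.05 analysis is strong, but it remains an inference.

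**3. Error rate if the listed primaries were co-equal**

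Assumption, not in the plan: each is tested at two-sided 0.05 and any one can support a claim. For k independent tests the false-positive chance is 1 − 0.95^k.

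- k = 4: 1 − 0.95⁴ = 0.185
- k = 3 (cost described, not tested): 1 − 0.95³ = 0.143

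For equally correlated normal test statistics, by numerical integration:

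| Correlation | k = 3 | k = 4 |
|---|---|---|
| 0.3 | 0.136 | 0.174 |
| 0.5 | 0.125 | 0.156 |
| 0.9 | 0.084 | 0.094 |

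**4. What an equal split would cost**

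At 0.05/4 = 0.0125 per outcome, power for abstinence with 120 per arm falls from 0.825 to 0.651.

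**The case against.** The best defence is that the primary outcome is evident. Section 3 attaches the word to abstinence, Section 6 sizes abstinence at the end of eight weeks, and the numbers reproduce from it without help from any other outcome. In Section 3, additional may mean only further, and the study is a pilot with a feasibility focus. Much of this stands: a reader would probably guess the intended primary correctly. It does not remove the contradiction on cost or supply a testing rule, and a plan that powers a 0.05 test should not leave its outcome to inference. Section 3's phrase may also mean primary within the substance-use domain only, which weakens it as a declaration.

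A reader might infer more than the documents support:

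- That the plan runs four tests at 0.05 with a 19% error rate. It does not say each will be tested or that any one suffices.
- That control-group access or wider adoption depends on a significant result. Section 7 says only that controls may get access if positive effects are verified on PEI, and describes adoption as a goal. Neither is a significance rule.
- That no time point is given at all. Eight weeks and six months both appear; what is missing is which is primary.
- That weeks 4 and 8 are the only treatment-period assessments common to both arms. That follows from Section 5, but Section 3's weekly questionnaire says otherwise.
- That the four population analyses must lose standing. That is a separate design choice, not needed to settle the outcome ranking.

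**Conclusion.** The concern holds as an inconsistency in ranking and a missing declaration, and it should be corrected. Sections 3 and 6 contradict each other on implementation cost and nearly do so on medical use. Section 6 lists at least four co-equal primaries while sizing one. Percent days abstinent at eight weeks is strongly implied as the outcome of the combined analysis, with 82% power at 120 per arm before dropout, but neither it nor its time point is designated, and there is no multiplicity rule.

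The possible inflation is up to about 19% for four outcomes and 14% for three. It is conditional on testing each at 0.05 and accepting any one, with independent tests as the upper end; positive correlation lowers it. The power figures assume equal allocation, two-sided tests and the plan's own effect and SD. The textual conflict depends on none of these assumptions.

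**What to change.** Before outcomes are examined by arm, amend Sections 3 and 6 so that they agree:

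1. Name one primary outcome for the combined 240-participant analysis: percent days abstinent from all drugs, as a level at the eight-week end point used for sizing, compared between arms at two-sided 0.05.
2. Reconcile the questionnaire descriptions in Sections 3 and 5 (who delivers them, and how often in each arm). Take the primary outcome from assessments scheduled identically in both arms, and state one recall window for both.
3. Label retention, health and service use, cost and six-month abstinence as secondary, reported with 95% confidence intervals. If a confirmatory claim on retention or six-month abstinence is wanted, test it after the primary in a fixed order, each at 0.05 only if the one before succeeded.

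The amendment is to text only, provided that the questionnaires (attached to the protocol but not seen here) ask the abstinence items over the same window in both arms. Section 5 says they are identical apart from the program sections. The cost is that retention, health and cost lose any stand-alone primary claim; the plan states no power for any of them, although retention is one of its main arguments for the program. The equal split at 0.0125 each would keep all four as primaries, but with the loss of power for abstinence shown above.

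### The 0.8 power is for the week-8 level of percent days abstinent, but section 6 lists changes in drug use as primary and names no analysis adjusted for use at entry

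*Combined protocol and SAP*

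**What the plan says.** All references are to the combined protocol and SAP.

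- **Power basis (section 6, Analysis of Data).** The quantity planned on is "the average drug use measurement (measured by the percent days abstinence from all drugs"). The planning values, taken from three earlier trials, are that the average in "the test groups was 75% and control group 66% with a common standard deviation of 24% at the end of the eight week trial". The claim examined here is "an alpha 0.05 and a power of 0.8 for combined analysis", which pools "all 240 participants across the four trial settings".
- **Primary outcomes (section 6).** "Primary outcomes measured include retention, changes in drug use, changes in health", followed by implementation costs. No reference value, time point or formula is given for the change in drug use.
- **Section 3 (Background, Rationale and Statement of Research Question(s)).** The primary substance-use outcome is described as abstinence by self-report. The list of what the analysis will focus on refers to levels of use, not changes.
- **Analysis method (section 6).** One- and two-way ANOVA where appropriate, following the earlier trials. No model adjusted for use at entry is named.
- **Entry data.** Section 4 (Subject Selection) admits "any consenting individual who reports substance abuse in the past thirty days". Section 5 (Research Plan) schedules control questionnaires at weeks 4 and 8 and a six-month follow-up. It describes no entry measurement, although the questionnaires are attachments that are not part of the text reviewed.

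**The concern.** A level and a change from entry are different variables with different SDs. The planning figures describe a level, and the protocol gives no entry SD, SD of change or entry-to-week-8 correlation. An analyst who takes the section 6 outcome list literally could test raw change scores by ANOVA. The power of that test is not the stated 0.8, and it can be lower than the power from ignoring the entry value altogether. An analyst who follows section 3 would test a level. The choice affects power, and the plan does not fix it before data are seen.

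**Working it through.** **Inputs from section 6:** difference 75 − 66 = 9 points; SD 24; alpha 0.05; 240 participants.

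**Assumptions not in the documents:** 120 per arm (1:1 allocation), two-sided test, entry SD 24, and a correlation rho between entry and week 8, shown over a range. Complete data are assumed first, then the 77% eight-week retention quoted in section 6.

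**Formula (normal approximation):** power = Φ(9 / (SD × √(2/n)) − 1.96), with n per arm.

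**Step 1: the plan's own figure.** For the week-8 level with n = 120, 9 / (24 × √(2/120)) = 2.905. Then 2.905 − 1.96 = 0.945, and Φ(0.945) = 0.828 (0.825 by the noncentral t). The stated 0.8 is met for the level with all 240 participants.

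**Step 2: change score against entry-adjusted level.**
- SD of change = 24 × √(2(1 − rho))
- Residual SD after adjustment = 24 × √(1 − rho²)

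| rho | SD of change | Power, change | Residual SD | Power, adjusted level |
|---|---|---|---|---|
| 0 | 33.9 | 0.537 | 24.0 | 0.828 |
| 0.2 | 30.4 | 0.632 | 23.5 | 0.842 |
| 0.3 | 28.4 | 0.690 | 22.9 | 0.861 |
| 0.4 | 26.3 | 0.755 | 22.0 | 0.887 |
| 0.5 | 24.0 | 0.828 | 20.8 | 0.918 |
| 0.7 | 18.6 | 0.963 | 17.1 | 0.982 |

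The noncentral t gives values up to 0.004 lower (0.752 for the change score at rho 0.4).

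**Step 3: where the change score reaches 0.80.** The largest SD allowed is 9 × √(120/2) / (1.960 + 0.842) = 24.88. Then rho = 1 − (24.88/24)²/2 = 0.463, or 0.467 by the noncentral t. The SD of change equals 24 only at rho = 0.50; at 0.47 it is 24.7.

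**Step 4: how far that threshold moves.** With entry SD s, the SD of change squared is 24² + s² − 2 × rho × 24 × s. Setting this to 24.88² = 619 gives:
- s = 18: (576 + 324 − 619) / 864 = 0.325 (about 0.33 with the t)
- s = 30: (576 + 900 − 619) / 1440 = 0.595, about 0.60

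With 77% retention, n = 0.77 × 120 = 92.4 and the allowed SD falls to 21.84. With entry SD 24 the threshold is then 0.586 (0.59 by the t). A one-sided test with the same retention would put it at about 0.475.

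**Step 5: 77% retention, two-sided.** The unadjusted week-8 level has power 0.722. Adjusted for entry at rho 0.5 it has 0.837. The change score at rho 0.3 has 0.577.

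**The case against.** The strongest reply is that the protocol never commits to a change-from-entry analysis. Section 3 speaks of abstinence and of levels, and its list of analysis topics matches the four primary outcomes of section 6 item by item. Section 6 itself calls percent days abstinent the drug-use measurement. The change is not defined as week 8 minus entry, no entry measurement is described, and the list of methods is open-ended. On that reading the powered variable is the primary one, and the looseness lies in a single word.

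Much of this stands. A reader might infer that the named primary outcome is a change score, so that the trial is underpowered unless the correlation is at least 0.47. The documents do not support that. Changes in drug use is one of several listed outcomes, section 3 words it differently, and no change score is specified. The 0.47 is also not a property of the plan: it needs entry SD 24, a two-sided test and no dropout. Equal SDs at entry and week 8 are themselves doubtful, since everyone enrolled has recent use and some are moving out of inpatient care.

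The reply does not settle which variable is primary, at what time point, or by which model. Sections 3 and 6 still read differently, and an unadjusted ANOVA remains the only method named.

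**Conclusion.** The concern holds as an endpoint that is worded inconsistently and not tied to its power basis, together with a missed gain in precision. The stated 0.8 describes the week-8 level. Read as a raw change score, the same outcome would have power of about 0.63 to 0.75 for correlations of 0.2 to 0.4, and would match the level only at 0.5, under the assumptions listed above. Adjusting the week-8 level for use at entry never does worse than about 0.83 under those assumptions. With 77% retention, adjustment at a correlation of 0.5 lifts power from about 0.72 to 0.84. Low power is not demonstrated, because neither the correlation nor the entry SD is in the documents and a change analysis is not specified. This is an inexpensive improvement worth making before analysis.

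**What to change.** In section 6, replace the entry for changes in drug use with: *percent days abstinent from all drugs at the end of week 8 (the measure and time point used for the power calculation), compared between arms by analysis of covariance with number of days of use in the 30 days before entry as covariate.* State that 75%, 66% and SD 24 refer to this week-8 level, and align the wording of section 3. An average over all eight weeks should not be substituted without confirming that these figures apply to it, since they are given for the end of treatment.

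Record the 30-day day count before randomization, alongside the existing eligibility question about the same period.

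If a change score is kept, define its reference value, state its SD or the assumed correlation, and restate the power.

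The cost is one extra number at entry, a few sentences in sections 3 and 6, and a little more analysis work, with no added participants or visits. The size of the gain depends on how strongly the 30-day count correlates with the week-8 outcome, which the documents do not give.
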